4.2.4 Subgroup analyses

The analysis will include three pre-defined subgroup analyses for the primary and key secondary outcomes according to 1) participants with high baseline impulsivity (based on delay discount task or self-report (S-UPPS); 2) participants with low perceived danger (defined as those who report No danger associated with target vehicle risk); and 3) participants with low perceived control (i.e. disagree with being able to control behavior). These cut-off were chosen to represent a population with the highest predicted likelihood of injury due to vehicle risks. The trial is not powered to detect subgroup differences and these will be considered exploratory and hypothesis generating.

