4. SAMPLE SIZE CALCULATION AND STATISTICAL ANALYSIS PLAN

4.1 Sample size calculation

The study has been powered to have at least 80% power for the primary outcome for Cohort 1 (seat belt use). Based on Sommers et al., 2013, we can likely expect the intervention to increase the percentage of subjects reporting seat belt use by15% on top of self-monioting alone. Using a 2-sample test of proportions, estimating 25% of the intervention participants and 10% of the control (SMS self-monitoring) report always seat beltuse, we would need around 100 subjects per group to show a significant difference between arms. Expecting 10% drop-out in the SMS 2-week run-in and 80% completing 8-week assessments, 300 enrolled in the ED should provide an analyzed sample of 216 (108 per arm).

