4.2 Statistical analysis plan

4.2.1 General considerations

The statistical analyses and reporting will adhere to the CONSORT guidelines. All tests will be twosided, a p-value < 0.05 will be considered significant, and all confidence intervals will have 95% coverage. All analyses will be conducted on a modified intention-to-treat basis only including participants responding to at least one week of SMS assessments during the intervention period. The two groups will be compared in relation to baseline characteristics using descriptive statistics. The persons conducting the statistical analysis will be blinded to the randomized allocation. Groups will be designated as "A" and "B" until all pre-specified analyses are performed and shared with all authors.

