4.2.2 Primary Analysis

At baseline, all participants (based on screening criteria) all had the risk factor. At subsequent time points, participants are analyzed as having/not having the same risk factor by randomized group. For our primary analysis, we will examine the proportion of participants in each group (SMS intervention; assessment control) who report the risk behavior using a chi-squared test of proportions. We will then perform a logistical regression, entering any baseline attribute that has univariate association with the outcome in the final model. We will report the difference in percentage with primary outcomes as well as odds ratios (from logistical regressions) with 95% confidence intervals The α level is set at .05 for all statistical tests.

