4.2.5 Statistical stopping criteria

There will be no formal stopping criteria for efficacy. There will be no predefined stopping criteria for futility since enrollment of the full cohort might allow for detection of efficacy in subgroups or in other outcomes even if the primary outcome is negative.

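### The exploratory subgroup plan names no treatment-by-subgroup interaction and lets high impulsivity rest on either of two instruments, while 4.2.5 looks to subgroup efficacy if the primary is negative

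*Combined protocol and SAP*

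**What the plan says.** Section 4.2.4 announces three pre-defined subgroup analyses for the primary and key secondary outcomes. The groups are "participants with high baseline impulsivity (based on delay discount task or self-report (S-UPPS"), participants who see no danger in the target behaviour, and participants who disagree that they control it. The section says that cut-offs were chosen, but it gives none for impulsivity. It also says that the trial is not powered for subgroup differences and that these analyses are exploratory and meant to generate hypotheses.

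No subgroup test or model is named. The only interaction in the plan is time by treatment, in the GEE of 4.2.3.

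On error rates, 4.2.1 says "All tests will be twosided, a p-value < 0.05 will be considered significant", and 4.2.2 says "The α level is set at .05 for all statistical tests". Section 4.2.5 explains the absence of a futility rule by saying that enrolling the full cohort "might allow for detection of efficacy in subgroups or in other outcomes even if the primary outcome is negative".

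**The concern.** The useful question is whether impulsivity, perceived danger or perceived control changes the effect of the intervention. A p-value from inside one group does not answer it, because nothing is compared with the remaining participants. A reader left with 4.2.4 as written would most naturally test each high-risk group alone at .05.

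The impulsivity definition adds a free choice. Delay discounting is a monetary choice task (section 2.8) and S-UPPS is a questionnaire (Baseline Questions appendix), so they can select different people. Without a governing measure or cut-off, the subgroup could be settled after results are seen.

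Sections 4.2.4 and 4.2.5 also pull in different directions. One treats subgroup findings as hypotheses; the other presents subgroup efficacy as something a negative trial might still deliver. At stake is how a subgroup result in a manuscript would be read, not the primary result.

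**Working it through.** **Inputs from the documents.** Two-sided alpha 0.05 (4.2.1, 4.2.2). Always-belted 25% versus 10%, about 100 per group, 216 analysed or 108 per arm (4.1). The primary outcome is the complement of always-belted (75% versus 90% reporting the risk), which leaves the test unchanged. Of the key secondary outcomes, only week 14 is a comparison between arms; the feasibility and acceptability percentages are not.

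**Inputs assumed.** The documents give no subgroup prevalence or correlations. I take subgroup shares of 10% to 50%.

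**1. The plan's own figure.** With pooled variance and mean rate 0.175:

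n = [1.96 × √(2 × 0.175 × 0.825) + 0.8416 × √(0.25 × 0.75 + 0.10 × 0.90)]² / 0.15² = (1.053 + 0.443)² / 0.0225 ≈ 99.5, so 100 per group. This matches 4.1. Attrition: 300 × 0.9 × 0.8 = 216. Power at 108 per arm is 83.1%.

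**2. Power inside a subgroup for the planned effect.** Power(n) = Φ[(0.15 × √n − 1.053) / 0.527]

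| Share of sample | n per arm | Power |
|---|---|---|
| 10% | 11 | 15% |
| 25% | 27 | 30% |
| 50% | 54 | 54% |
| 75% (complement of 25%) | 81 | 71% |

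**3. Same true effect in everyone.** With power a in the subgroup and b in the complement, the two tests disagree with probability a(1 − b) + b(1 − a).

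- 50% share: 2 × 0.537 × 0.463 = 0.497.
- 25% share: 0.302 × 0.287 + 0.713 × 0.698 = 0.086 + 0.498 = 0.585.

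At the 25% share, most of the disagreement is a significant complement beside a non-significant subgroup, so the misleading result is often a falsely empty subgroup. An interaction test would signal a difference that does not exist at its nominal 5%.

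**4. False positives with no effect anywhere, Cohort 1, one outcome.** Under independence: 1 − 0.95³ = 14.3% with one impulsivity definition, and 1 − 0.95⁴ = 18.5% if both are tried. A simulation used 20,000 null trials per setting, 108 per arm, a 17.5% rate in both arms, shares of 25% or 50%, correlation 0 to 0.6 between the two impulsivity measures, and danger and control independent. It gave:

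- impulsivity alone: about 5% with one measure, 8.5% to 9.7% with either;
- any of the four tests: 15% to 18%;
- any of the four, given a non-significant overall result (the situation 4.2.5 has in mind): 12% to 16%.

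Adding week 14 as if independent gives 1 − 0.95⁸ = 33.7%. That is an upper figure, since the two time points should be positively correlated.

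**5. What an interaction test could detect.** Suppose the 15-point effect exists only in the subgroup and the rate is 10% elsewhere. On the risk-difference scale with a 50% share, SE = √(0.2775/54 + 0.18/54) = 0.092, z = 0.15 / 0.092 = 1.63, power 37%. With a 25% share, SE = √(0.2775/27 + 0.18/81) = 0.112 and power is 27%. With a 10% share it is 15%.

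**The case against.** The strongest reply is that 4.2.4 already contains the safeguard. The subgroups are three, named in advance, declared unpowered and labelled exploratory. That stands, and it is why this is a minor point.

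Four stronger readings are tempting, and the documents do not support them.

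- A reader might infer that the plan prescribes tests inside each high-risk group. It does not: no subgroup method is stated. The remark that the trial lacks power for subgroup differences fits a between-group contrast at least as well. What can be said is that the method is unspecified and that one-level definitions point to within-group tests.
- A reader might infer that 4.2.5 licenses an efficacy claim in a subgroup, or continuation after a failed primary. The sentence only explains why there is no futility rule, it names other outcomes as well as subgroups, and no interim efficacy analysis is described. It is loose wording, not a reporting rule.
- A reader might apply the false-positive figures to all three cohorts. The 216 belongs to Cohort 1. Cohorts 2 and 3 enrol 100 each and are exploratory as a whole (2.1). With the same attrition, which is an assumption, 100 × 0.9 × 0.8 = 72 would be analysed, or 36 per arm, and a 25% subgroup would have 9 per arm.
- A reader might expect interaction tests to cure the multiplicity. Three interaction tests at .05 carry the same 14.3% under independence. They guard against false claims of a differing effect, which is a separate problem.

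The word joining the two impulsivity instruments could also mean one combined definition. If so, the combination rule is missing.

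**Conclusion.** The point holds as a low-cost clarification of declared exploratory analyses; it does not touch the primary analysis. As written, the plan gives no way to assess the subgroup differences that 4.2.4 mentions, leaves one of three subgroups undefined, and uses wording in 4.2.5 that sits awkwardly with 4.2.4.

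If within-group tests were used, subgroup and complement would disagree on significance about half the time or slightly more (50% to 58%) under a common effect. Trying both impulsivity measures would put the chance of some false-positive subgroup in Cohort 1 at about 15% to 18% for one outcome, against roughly 13% to 14% in the same simulation with a single measure. The second instrument is therefore a modest part of that total; most of it comes from having three factors.

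These figures rest on assumed subgroup shares of 25% and 50%, the assumed correlations, and 4.1's rates and attrition. Very small subgroups, which are plausible for participants who see no danger at all, would change them.

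**What to change.** 1. In 4.2.4, for each pre-defined factor S, fit logit(p) = b0 + b1·arm + b2·S + b3·arm×S. Report exp(b3), exp(b1 + b3) for the subgroup and exp(b1) for its complement, all with 95% confidence intervals. State that no efficacy claim will rest on a within-subgroup p-value.
2. Name one governing impulsivity measure, with a cut-off or as a continuous score, and use the other as a sensitivity analysis. The documents give no ground for preferring either, so the choice is the investigators'. Record it before unblinding. Because 4.2.1 keeps the A and B labels until the pre-specified analyses are done, the record should precede any comparison by group, even a masked one.
3. Keep the plan's cut-offs for danger and control, since 4.2.4 chose them to target those at highest predicted risk. Ordinal scores can be an optional sensitivity analysis.
4. Correct the control_dd item. In the baseline, 8-week and 14-week appendices it repeats the typing-while-driving wording, so as printed the low-control subgroup in Cohort 3 is not about drink driving. If it was fielded as printed, drop that subgroup for Cohort 3.
5. Reword 4.2.5 so that subgroup findings after a negative primary are called hypothesis generating, as in 4.2.4.

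The cost is a few model terms and some text, on data already planned for collection; only the item correction changes an instrument. The downside is imprecision (interaction power of about 15% to 37% in the cases above), and the change does not control multiplicity, so the number of subgroup tests run should be reported with the results.

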4.2.5 Statistical stopping criteria

There will be no formal stopping criteria for efficacy. There will be no predefined stopping criteria for futility since enrollment of the full cohort might allow for detection of efficacy in subgroups or in other outcomes even if the primary outcome is negative.

5. DATA COLLECTION AND MANAGEMENT

5.1 Data collection process

Data collection will be the responsibility of the individual site investigators with oversite from the trial coordinating center. All baseline and outcome variables (i.e. demographics, vehicle risk behaviors) will be obtained prospectively from electronic surveys. Data will be entered directly into the online database software (see below).

5.2 Variables

Measure library is included in the Appendix.

5.3 Data quality and validity

Data quality and validity will be optimized by using a detailed data dictionary which will be distributed to all sites. Data quality will be monitored both centrally by the coordinating site and locally by each site principal investigator.

5.4 Data storage and security

All data will be stored and secured by [name], the Director of the Office of Academic Computing (OAC) at Western Psychiatric Institute and Clinic (WPIC). Baseline data will be entered into *Web Data Xpress*, a web-based data entry system that enables users to add and edit records in a database. By using Secure Sockets Layer (SSL) and user authentication, users can be assured that data transmitted over the internet is safe and secure. The system to send, receive and process text messages, was developed on the OAC SQL Server 2005 system with permissions granted to specific EM faculty and staff to access the data for a given project through a Microsoft

SaVE Trial Protocol v.1.0 Page **18** of **36** Access front-end. Through these mechanisms, as well as relevant training for all involved parties, participant confidentiality will be safeguarded.

The consent form and other trial documents for each participant will initially be stored in a secure, locked place at the individual sites. Participating sites will be responsible for maintaining their own trial documents and study materials. Trial documents generated at the Coordinating Center will be maintained the Coordinating Center. Following completion of the trial, documents will be maintained for a period of at least 7-years at each site (or longer depending on local IRB guidelines).

6.1 RISKS TO HUMAN SUBJECTS

Information obtained at the time of screening and assessment may pose psychological risks and some of the questions may be considered sensitive in nature and may cause emotional distress. We will be collecting information that if disclosed could have adverse consequences for subjects or damage their financial standing, employability, insurability, or reputation. Additionally, we are enrolling underage individuals, which risk disclosure of illegal activity associated with alcohol and/or drug use. Participants face some risk of loss of confidentiality due to the nature of data acquisition through the internet and cell phone SMS. First, participants may have information on their mobile phone that is seen by someone else. As well, there may be the rare risk that someone not associated with this research sees their medical record or data as a result of their participation in this research. Overall, the likelihood of any of these risks causing a subject any serious discomfort or inconvenience is very low. Confidentiality of information will be maximized in accordance with HIPPA regulations.

6.2 ADEQUANCY OF PROTECTION AGAINST RISK

6.2.1 Recruitment and Informed Consent: Eligible patients will be identified by a Research Associate with clinical appointments at enrolling hospitals. The RA will conduct confidential screening of ED patients during breaks in patient medical care. All responses to screening questions will be recorded on a secure web site. The Primary Investigator will audit screenings and will be available to the RA during screening. The RA will approach all permission-granting, potentially eligible patients to obtain informed consent for study screening. To ensure privacy, family or other individuals accompanying the patient will be asked to leave the area prior to the screening procedures and patients will be reminded that other people may be able to overhear the conversation. The RA will provide tablet computer for participants to complete screening questionnaire immediately after informed consent. Screening will include review of inclusion/exclusion criteria and basic demographic information to determine how those who screen positive differ from those who screen negative. Interested and eligible individuals will be asked to complete written informed consent. The computer shows the RA whether the participant is eligible or not, and whether the risks were present or not. The RA will then read a standard script based on eligibility and offer eligible patients study participation, obtaining written informed consent. The RA will present an oral and written description of the study as part of informed consent, including a description of the project procedures, potential risks and benefits, and confidentiality. The RA will review any questions the patient may have during the consent process. Patients will be informed that they will be compensated for their time during the research assessments.

6.2.2 Protection Against Risk: In order to protect study participants form potential risks related to the loss of confidentiality and due to any discomfort that they may experience in answering any questions, the following steps will be taken: 1) Patients will be told that they can withdraw from the study at any time by contacting us. 2) All information provided by the patient will be referenced to a subject ID# and will be kept in locked file cabinets. The patient's ID# can be connected to the subject's name only through a single master file, accessible only by the Primary Investigator. All data and files will be entered on computers protected by passwords and stored in a locked office. 3) All research staff will be trained in the importance of maintaining confidentiality and will undergo annual mandatory training of human subjects research. 4) All patient data will be presented in aggregate and no individuals will be identified individually. Additionally, we will make every effort to ensure that subject information is protected so only

SaVE Trial Protocol v.1.0 Page **19** of **36** authorized persons can see their information. All messages sent from subjects to our phone number will be catalogued and encrypted, stored per UPMC security standards. All participants will be advised to set up password protection on their cell phones and to erase messages after responding to minimize the chance of loss of private information. We state explicitly in the consent that we will not be able to respond in real-time to any concern a patient has that is outside the expected responses that is sent to our phone number, nor any text message outside the scope of the question we ask. Immediate or emergency text-messages that are received and outside the scope of the questions we sent will all receive a standardized text message, stating "We appreciate your participation. If you have an emergency, please call 911." As well, all messages are archived in our database and will be reviewed at least every 2 days by the investigators. At the end of this study, the data key will be destroyed.

6.2.3 Certificte of Confidentiality: Because we are collecting data that is sensitive, we will seek a Certificate of Confidentiality from the NIH.

6.2.4 Potential Benefits to Individual Participants: All participants (and those who screen positive) will be offered an informational sheet on vehicle risks. Particiapnts in both treatment arms will also be prompted to self-monitor their vehicle risks over a period of 14 weeks, which also will likely result in reduced risks thorugh assessment reactivity and awareness. Assuming our hypothesis is correct, individual participants enrolled in our study and randomized to the treatment arm will also benefit in learning improved vehicle safety behaviors.

6.2.4 Potential Benefits to Society: Risky vehicle behaivors are associated with increased probability of serious injury due to motor vehicle crashes. No current existing behavioral support tool exists to reduce these risky behviors. Our study, assuming our hypothesis is confirmed, will provide strong support for the widespread adoption of an SMS program for young adults with these risks. This, in turn, could significantly reduce the global burden of injury-related morbidity and mortality.

7. MONITORING

7.1 Institutional Review Board (IRB)

The study will be reviewed and approved by the IRB at each participating site.

7.2 Data Safety and Monitoring

The proposed study will be monitored to enhance the safety of study participants. Although minimal risks are expected for participants in the study, all data and research enrollment processing will be audited at least monthly by the Departmental Clinical Research Meeting (DCRM) of the Department of Emergency Medicine. This DCRM includes senior researchers in the Department of Emergency Medicine and is responsible for continual review of all non-exempt studies involving patients. At least one investigator of this study will attend these meetings. All members of the DCRM have considerable research and clinical experience to evaluate the study's recruitment and retention procedures, to monitor any potential significant benefits or risks that may occur so as to warrant the early termination of the study and to monitor study progress. Additionally, bi-weekly meetings will be held with primary investigators and research assistants to review research process. Any significant issues or variations from protocol related to this study will be reported to Department of Emergency Medicine DCRM and to the University of Pittsburgh Institutional Review Board in a timely fashion. Upon study renewal, a monitoring report will be provided to the IRB.

8. TIMELINE AND ENROLLMENT 8.1 Timeline

Pre-Months 12-18 Months 19-24 Months 0-6 Months 7-12 trial Funding **Protocol development** Creation of data dictionary Clinicaltrials.gov registration Ethical approval Creation of randomization list Site start-up (Pitt) Site start-up (Penn) **Cohort 1 Enrollment Cohort 1 Follow-ups Cohort 2 Enrollment Cohort 2 Follow-ups Cohort 3 Enrollment Cohort 3 Follow-ups DSMB** monitoring Cleaning and closing of the database **Unblinding & Data analysis** Main manuscript writing Publication and presentation of results

8.2 Screening & Enrollment

Enrollment at each site will be continuously monitored by the site investigator and the principal investigator. Each site will maintain a screening log including all participants who meet all eligibility criteria at that site. A standardized screening log will be kept using WebDataXpress, thus allowing for continuous updating of the screening log and will allow capture of all screening failures.

Enrollment will be competitive (i.e. without specific enrollment caps). Number of enrollments at each site will be shared with all sites on a monthly basis. Sites will be expected to complete all elements of the online screening and enrollment forms for each subject. In the case that a site continuously underperforms despite troubleshooting and feedback, the Investigators will evaluate whether enrollment will continue at that site.

